**Cognitively Augmented Behavioral Activation for Veterans with Comorbid mTBI/PTSD**

**Protocol #: [Version 14, 8/12/2020]**

**Funding Agency: RR&D Merit Review**

**Principal Investigator/Study Chair: [name] and [name]**

## Abstract

Veterans returning from the current conflicts in Iraq and Afghanistan exhibit high rates of comorbid mTBI/PTSD. Given the comorbidity and neuropsychiatric symptom overlap of these disorders, it can be difficult to determine whether problems and disruptions in functioning are due to mTBI, PTSD, or both. Hence, it is challenging for providers to know how to prioritize these patients' clinical issues and how to effectively treat them. Currently, there are no evidence-based treatments for comorbid mTBI/PTSD. Further, it is unclear to what extent existing treatments for each disorder can be adherently and effectively implemented for the other. As such, most current treatment recommendations suggest a holistic or integrated approach to treatment for comorbid mTBI/PTSD targeting symptoms and functionality rather than underlying etiology. We are proposing a treatment for comorbid mTBI and PTSD that directly targets daily functioning and quality of life. The primary objective of this study is to evaluate the efficacy of Cognitively Augmented Behavioral Activation (CABA), a new hybrid treatment for veterans diagnosed with comorbid mild Traumatic Brain Injury (mTBI) and posttraumatic stress disorder (PTSD). The study's specific goals are to determine whether: 1) CABA reduces PTSD symptoms in veterans with mTBI/PTSD, 2) CABA reduces cognitive-related functional impairment in veterans with mTBI/PTSD, 3) CABA results in improvements in depression symptoms, cognitive functioning, and quality of life in veterans with mTBI/PTSD; and 4) CABA is an acceptable treatment for veterans with mTBI/PTSD. The overall goal is to develop an evidence-based manualized treatment for comorbid mTBI/PTSD that can be readily implemented in Veterans Health Administration (VHA) treatment settings. The study design makes use of the convergent availability of resources at the two participating Veterans Administration Medical Centers (VAMCs) in Portland, Oregon, and Seattle, Washington to conduct a Randomized Controlled Trial (RCT) of CABA. The study will recruit a total of 192 veterans  $\leq 55$  years of age, 96 participants at each site, enrolled at participating VAMCs who are diagnosed with both mTBI and PTSD. Inclusion criteria will be 1) Veterans  $\leq 55$  years of age enrolled at one of the participating VA sites who are able to provide informed consent, 2) Diagnosis of PTSD based on the Clinician Administered PTSD Scale (Blake et al., 1990), 3) Positive screen on the Structured Interview for Collecting Head Trauma Event Characteristics as outlined by the VA/DoD Clinical Practice Guideline for Management of Concussion/mTBI and positively endorsed any of the Neurobehavioral Symptom Inventory (NSI) cognitive symptoms items (items 13-17), 4) English speaking, able to attend treatment (if in CABA condition) and assessment sessions, and willing to refrain from additional mental health treatment during the first 3 1/2 months of the active phase of treatment if they are assigned to the CABA condition, and 5) Willingness to participate in audio-recorded sessions. Exclusion criteria will be 1) Current diagnosis of moderate or severe substance (alcohol) use disorder using DSM-5 criteria within the past 30 days, 2) Current Bipolar or psychotic disorder (requirement to refrain from additional treatments might be harmful), 3) Veterans with a history indicated by medical record review of a diagnosis of moderate, severe, or penetrating TBI, or self-reported history on the Structured Interview for Collecting Head Trauma Event Characteristics of TBI with PTA greater than 24 hours or LOC greater than 30 minutes, 4) Active suicidal intent indicating significant clinical risk, which would suggest that a treatment specifically targeting this intent was indicated clients who report suicidal ideation without imminent risk will be admitted into the study, 5) Initiated psychotropic medication, including Prazosin, within 4 weeks or changed dosage within 2 weeks prior to the first assessment, as this would make it difficult to determine which treatment contributed to change in the CABA condition; additionally, started or changed dosage of sleep medication or low dosages of tricyclic antidepressant or trazodone for pain or sleep within 1 week prior to the first assessment. Participants could be re-considered for eligibility after stability on medication was achieved. Enrollees will be asked, but not prohibited, to hold the doses of the current medications stable over the course of enrollment (though changes in medications after enrollment will not exclude them from on-going participation), 6) Auditory or visual impairments that would compromise ability to participate cognitive rehabilitation group or benefit from compensatory strategies. Eligible participants will be randomly assigned to either the CABA or Treatment as Usual (TAU) group. Participants in the CABA group will receive the CABA intervention via telehealth (video or telephone) during the first 14 weeks of their participation in the study, whereas TAU participants will continue to receive TAU (usual care in a PTSD specialty treatment clinic, but no CABA) during their participation in the study. Both groups will undergo evaluations at baseline, 7 weeks (mid-treatment), and 14 weeks (post-treatment). During their study participation, all participants will continue to receive their usual medical care.

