Randomization procedures as well as overall multisite study interim and final data analyses will be conducted by our contracted statistician, [name] who is affiliated with University of California, San Diego. [name] will receive a “limited data set” copied in encrypted format sent via secure email. The “limited data set” is defined as such for inclusion of patient assessment dates and otherwise would be considered de-identified. A Data Use Agreement will be pursued between the VAPORHCS and [name] recognizing the agreement of the terms for use of this data which shall be transmitted and accessed strictly for data analysis purposes pursuant to the goals of this study.

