## **5.0 Study Procedures**

### **5.1 Study Design**

#### **Overall design:**

We propose a dual-site randomized controlled trial comparing Cognitively Augmented Behavioral Activation (CABA) with a treatment as usual control group (TAU). The study design makes use of the convergent availability of resources at the participating VAs (Portland and VA Puget Sound). VA Puget Sound has two divisions, Seattle and American Lake, and all study activities may take place at either division. Participants will be Veterans  $\leq 55$  years of age (both male and female) with comorbid mTBI/PTSD enrolled for outpatient medical services at these VAs. A total of 192 participants will be recruited, 96 at each site. As described in the “Overall Clinical Trial Plan” section, participants in CABA will receive the CABA intervention via telehealth during the first 14 weeks of study participation, whereas TAU participants will receive usual care (no CABA intervention) during study participation (but will be offered CABA at no cost after the end of the study). In order to adhere to a national VA performance measure that requires 8 sessions to be delivered over a 14-week period, participants will be contacted by phone by a blinded assessor for the mid-treatment assessment 7 weeks after the onset of treatment. Allowing 14 weeks to complete a 10-session treatment protocol accounts for cancellations and missed sessions. Participants will then be seen for a follow-up assessment 14 weeks after initiating treatment. During their study participation, all participants will continue to receive their usual medical care. Due to the COVID-19 pandemic and hospital restrictions for in-person visits, all study operations will be conducted remotely. A detailed description of this plan is described in the following section.

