**Clinical** providers may refer interested patients and document their willingness to be contacted by the study through CPRS via their progress notes and using templated language provided to them (See Appendix G). Clinicians may also send referral information via encrypted email with the same templated documentation (or comparable documentation that the Veteran is interested in hearing more about the study and gives permission for research staff to contact them). Following a chart review and preliminary phone screen to determine eligibility, potential participants will be scheduled for an initial telehealth (by video or telephone) appointment during which they will be consented to the study. Consented participants will be instructed to return the informed consent form (ICF) and Authorization for Use and Release of Individually Identifiable Health Information Collected for VHA Research (HIPAA form) to the study team using a prepaid and preaddressed envelope. Once received, a study team member will complete an assessment appointment with the participant via telehealth. After all eligibility criteria are met and the assessment is complete, if telehealth appointments are conducted via VA Video Connect (VVC) platform, participants may receive automated reminders and appointment links over email, consistent with procedures for clinical appointments using VVC. The study statistician will randomly assign eligible participants to one of the two treatment options and will notify the site study coordinator about randomization status. The site study coordinator or other appropriate research team member, will contact the participants to inform them of their group assignment. Those assigned to CABA will be contacted by their therapist and tele-or video-therapy will commence. Those assigned to TAU will be offered a referral for PTSD specialty care. The assessors will be blind to group status throughout the study whenever possible. Consistent with a national VA performance measure that requires 8 sessions to be delivered over a 14 week period, participants will be contacted by phone by a blinded assessor for the mid-treatment assessment 7 weeks after the onset of treatment. Allowing 14 weeks to complete a 10 session treatment protocol accounts for cancellations and missed sessions. Participants will then be seen for follow-up assessments 14 weeks after initiating treatment. In order to minimize drop-out and maximize retention of individuals for intent-to-treat analyses, extensive efforts will be made to stay in contact with all study participants, including individuals who drop out of treatment. CABA participants who are deemed nonresponders or relapsers (do not evidence at least a 20% reduction in PTSD or cognitive symptoms) at the post-assessment or follow-up assessment (or an increase in suicidality or substance abuse), and other participants as clinically appropriate, will be offered alternative treatment or appropriate referrals.

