## 5.5 Study Evaluations

### **Visit schedules**

#### **Pre-enrollment screening:**

- 1) Medical Record Review: Study personnel will review each participant's medical record, including their neuropsychological assessment records, to document severity and type of current cognitive status, medical and psychiatric history, current treatment, and medications.
- 2) Clinical Screening Phone Interview: Study personnel will conduct a brief phone screening to ensure subjects meet initial eligibility criteria. Participants interested in the study will be asked to provide an email address for scheduling video telehealth appointments.

**Study Enrollment:** All eligible participants will complete a consent visit including:

Informed Consent: Study personnel will complete consent procedures. All effort will be made to ensure participants fully comprehend study procedures, risks, and benefits.

**Baseline Assessment:** All eligible participants will complete a baseline assessment visit including:

Baseline Psychological and Cognitive Assessment Battery (see below). This includes assessment of exclusionary diagnoses as well a brief neuropsychological battery, diagnostic interviews, and self-report questionnaires of current emotional and post-concussive symptoms. If an individual is found not be eligible during this assessment, the assessment will be discontinued at that point.

**Treatment Visits:** All eligible patients will be randomized (CABA or TAU). CABA participants will be assigned to a therapist and receive the 10-session intervention (during COVID-19 this will be completed using telehealth modalities); TAU participants will be referred to PTSD specialty care.

**Mid-treatment Assessment:** Participants will complete questionnaires at mid-treatment (approximately 7 weeks after initiation of treatment) designed to assess current emotional and post-concussive symptoms.

**Post-treatment Assessment:** Participants will complete a brief cognitive assessment battery, diagnostic interviews, and questionnaires designed to assess current emotional and post-concussive symptoms (see section B “Data Collection and Assessment” below for a list and description of each battery measure). This will take place approximately 14 weeks after the initiation of treatment.

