*by a Westfall-Young procedure, we would include an alpha level of .04 for Hypothesis 1a, .03 for Hypothesis 1b and 2a, and .05 for Hypothesis 2b.* We estimate that with the proposed sample size of 192 (15% drop-out) patients (96 for each of the two groups), the study will have minimum power of 80% to yield a statistically significant result for a medium effect size. Hedker et al. defined medium effect size in this model as a between-group difference increasing linearly from 0 at baseline to .5 SD units at the last time point. Hypothesis 2b is a cross-sectional hypothesis using data collected only in the week 14 of the study. The proposed sample size will provided us with a minimum power of 90% to detect a medium to large effect size. The former and foundational Behavioral Activation for PTSD study by [name] and [name] yielded the following rates which also informed our proposed sample size determination: 192 screened, 81 enrolled, 10 dropped (12.3% dropout rate), 101 screen failures.

**Outcome analyses:** Data analyses will proceed in stages. Descriptive statistics and exploratory graphing such as frequencies, means, standard deviations, stem and leaf diagrams, and scatterplots will be used to assess normality of data in terms of presence of skew and/or outliers. Continuous outcome data will be transformed if necessary using an appropriate transformation such as the log transform for skewed long tailed data. Prior experience with this kind of data leads us to expect that for all variables, the distributions will be skewed and the variances not homogeneous. Similarly, potential covariates will be summarized with descriptive statistics and graphs to determine the most appropriate way to treat these variables (e.g., continuous, categorical, or interval representation). For outcome measures acquired at baseline, 7, and 14 weeks, the analytical approach will address the nature of the outcome, as well as accommodate the within

individual variability due to the repeated assessments. Results from will be inspected for bias due to drop-outs or missing data.

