**Hypothesis 1a)** PTSD symptom severity. Dependent variables: CAPS-V and PCL-5.

**Hypothesis 1b)** Functional impairment. Dependent variables: HVLTR, WAIS-IV (Digit Span subtest), DKEFS (Trails subtest), and COWAT (Verbal Fluency).

Independent variables: Treatment group (2 levels, CABA and TAU), & Time (3 levels, Weeks 0, 7, and 14). Statistical Analysis: We will analyze data on all randomized subjects in whom we have a baseline assessment and at least one post-baseline evaluation by Mixed effects model methods. Preliminary inspection of data will determine whether the outcome is nearly normal, or whether an appropriate transformation is required, or whether a generalized linear mixed model should be considered. The mixed effects model method provides an estimate of the individual variability around the population trend, the variability of the individual intercepts (baseline values) and slopes (changes across time), and the correlation between them. A fully saturated treatment by time model will be utilized for inference. Covariance structure will be chosen based on Akaike's Information Criterion (AIC). Random group level treatment effects will also be evaluated for importance based on the model AIC. This allows for any group level effects to be incorporated into the model. Denominator degrees of freedom will be calculated using the Kenward-Roger small sample correction. The design is a 2 (sites) X 2 (CABA vs TAU) X 3 (baseline, 7, and 14 weeks). The interaction of Site and Treatment X Site will be included and tested as

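### Week-7 and week-14 assessments are timed from treatment start, which is undefined for TAU, so time since randomisation may differ by arm

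*Combined protocol and SAP*

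**What the plan says.** Three procedural passages count from treatment start. Section 5.1, Overall design, says "Participants will then be seen for a follow-up assessment 14 weeks after initiating treatment". The Procedures paragraph of section 5.1 repeats this for week 14 ("Participants will then be seen for follow-up assessments 14 weeks after initiating treatment") and places the mid-treatment call seven weeks after treatment begins. Section 5.5, on the post-treatment assessment, says "This will take place approximately 14 weeks after the initiation of treatment". No visit window is given anywhere.

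For CABA, the Procedures paragraph has the therapist contact the participant and therapy begin. For the control arm it says "Those assigned to TAU will be offered a referral for PTSD specialty care". The Abstract describes TAU participants as continuing to receive usual care.

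Other places count by study week. The Abstract puts both groups' evaluations at baseline, 7 and 14 weeks. Table 3 sets week 0 at the screening and baseline visit, which precedes randomisation. The sample-size text describes hypothesis 2b as "using data collected only in the week 14 of the study".

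For hypotheses 1a and 1b, section 5.6 enters "Time (3 levels, Weeks 0, 7, and 14") in a saturated treatment-by-time model. The set analysed is randomised participants with a baseline and at least one later evaluation. Section 4.0 notes that the statistician's limited data set "is defined as such for inclusion of patient assessment dates and otherwise would be considered de-identified", but no planned analysis uses those dates.

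**The concern.** Treatment start happens after randomisation, and the arms reach it by different routes: direct therapist contact for CABA, a clinic referral for TAU. Hanging the outcome date on it can undo the equal follow-up that randomisation would otherwise provide. The model cannot see this, because an assessment done 14 weeks after randomisation and one done 18 weeks after it would both be labelled week 14. Any symptom change during the extra weeks in one arm would be counted in the treatment contrast.

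It also bears on who is analysed. Under the treatment-start clock, a TAU participant who never starts has no week 7 or week 14. A coordinator would have to invent a date or leave the assessment undone, and without a later evaluation that person leaves the analysis set. This works against the aim, in the same Procedures paragraph, of keeping participants for intention-to-treat analysis.

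**Working it through.** **No plan figure to reproduce.** The plan gives no figure for assessment timing. The only plan figure used here is the 0.5 SD difference at the last time point (section 5.6), as a yardstick. The stated 80% power is not in question on this point.

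**Step 1: apply each clock.** Let a CABA participant have a first session *s* weeks after randomisation and a TAU participant a first specialty visit *u* weeks after it.
- Treatment-start clock, TAU start read as first visit: CABA is assessed at *s* + 14 and TAU at *u* + 14. The gap is *u* − *s*.
- Treatment-start clock, TAU start read as assignment: CABA is assessed at *s* + 14 and TAU at 14. The gap is −*s*, so CABA is later.
- Treatment-start clock, TAU never starts: no due date.
- Table 3 weeks for everyone: all are assessed 14 weeks after baseline, with no systematic gap.

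The documents give neither *s* nor *u*, nor say which reading applies. Even the sign of the gap is open.

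**Step 2: illustrate the size.** Inputs are from Table 1 (the earlier BA trial, TAU arm): CAPS 79.4 (SD 16.0) before treatment, 62.6 (SD 27.5) after, 56.5 at three months; PCL 58.1 (SD 8.6) before and 49.8 after. Assumptions: 14 weeks from pre to post, 13 weeks from post to three months, linear change within each interval, and a gap of 2 to 4 weeks between arms.

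Slopes:
- before post-treatment: (79.4 − 62.6)/14 = 1.20 points per week
- after post-treatment: (62.6 − 56.5)/13 = 0.469 points per week

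Shift in SD units = slope × gap / SD.

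| CAPS slope and SD | 2 weeks | 4 weeks |
|---|---|---|
| Later slope, SD 27.5 | 0.938/27.5 = 0.034 | 1.877/27.5 = 0.068 |
| Earlier slope, SD 27.5 | 2.4/27.5 = 0.087 | 4.8/27.5 = 0.175 |
| Earlier slope, SD 16.0 | 2.4/16.0 = 0.15 | 4.8/16.0 = 0.30 |

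PCL on its baseline SD is close to the last row: (8.3/8.6)/14 = 0.069 SD per week, so 0.14 and 0.28.

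Against 0.5 SD, the post-treatment-SD figures are 7% (0.034/0.5) to 35% (0.175/0.5). The largest baseline-SD figure is 60% (0.30/0.5).

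**Step 3: direction.** After post-treatment, mean CAPS fell in TAU (62.6 to 56.5) but rose in BA (54.7 to 57.7). The effect of a late assessment therefore depends on which arm is late and on that arm's course.

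**Step 4: slack under a randomisation clock.** Ten weekly sessions need ten of the 14 weeks, leaving 14 − 10 = 4 weeks to start, or 15 − 10 = 5 if the assessment falls at the end of a 7-day window.

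**The case against.** The two clocks may be loose wording for one schedule. The Overall design paragraph itself places CABA in the first 14 weeks of participation and the assessment 14 weeks after treatment starts, as if these coincide. Since the Abstract has TAU participants continuing usual care, their start could be read as assignment. That does not settle it: if TAU starts at assignment and CABA at first session, the clocks still differ by arm.

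A second argument is that timing from treatment start is deliberate. The control-intervention text in section 5.1 aims to equate the amount of treatment, and a start-based clock gives every starter the same 14 weeks. This has force: counting from randomisation is a choice of estimand and has a cost. But the start-based clock offers nothing for people who never start, and it sits badly with the stated intention-to-treat aim.

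A third argument is that the size is conjecture. This stands. The gap and both intervals are assumed, Table 1 comes from a trial not restricted to veterans with mTBI, and the result nearly doubles with the choice of SD.

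A reader might infer more: that the arms will be assessed at different times, that the primary result is biased towards CABA, or that the error rate is inflated by a known amount. The documents support none of these. They give no start intervals, do not fix the direction, do not state whether the test is one- or two-sided, and leave open that sites will simply apply Table 3.

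**Conclusion.** The point holds as a conditional one. It is clear from the text that the procedures time both assessments from an event undefined for TAU, that other sections imply study weeks, that no rule reconciles them, and that the model uses nominal weeks only. Whether this produces unequal follow-up depends on how sites read the plan, so size and direction are unknown. If the procedures are followed, time since randomisation can differ by arm and TAU participants who never start have no due date. If Table 3 is applied to everyone, there is no gap.

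The shifts of about 0.03 to 0.17 SD (post-treatment SD), or up to about 0.30 SD (baseline SD), show only that a gap of 2 to 4 weeks would not be negligible beside 0.5 SD. They rest wholly on the assumptions listed. Because the correction is cheap, it should be made.

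**What to change.** 1. In section 5.1 (Overall design and Procedures) and section 5.5, count both assessments from the randomisation date in both arms: week 7 = day 49 ± 7 and week 14 = day 98 ± 7, whether treatment is waiting, under way, declined, stopped or finished. Table 3's baseline-visit weeks would also treat the arms alike. Randomisation is preferable because it is the point from which the arms can diverge.
2. Add a supportive PCL-5 analysis with actual days since randomisation as the time variable, using the assessment dates already in the statistician's data set. The model in section 5.6 stays the primary test. Do not add an elapsed-time covariate for CAPS-V: it is measured only at baseline and week 14, and such a covariate would be post-randomisation, undefined at baseline and entangled with arm.
3. Report by arm the days from randomisation to each assessment and to first session, sessions received, and the number who never started. The plan already undertakes to record all treatment received.

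The cost is wording in three places, one supportive model and one table, with no added visits.

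The downside is that late starters in either arm are assessed after less treatment. CABA participants who start more than about 4 weeks after randomisation cannot complete ten weekly sessions by day 98, and TAU participants facing clinic waits will have had fewer sessions. The contrast then includes access delay, as an intention-to-treat comparison with usual care should.
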